#### **FUNDER**

This trial is primarily funded by the National Institute for Health and Care Research (NIHR) Invention for Innovation (I4I) Product Development Award (PDA) programme.

## **Clinical Investigation Plan Information**

This Clinical Investigation Plan (CIP) describes the CASSETTE trial and provides information about procedures for entering participants. The CIP should not be used as a guide for the treatment of other non-trial participants; every care was taken in its drafting, but corrections or amendments may be necessary. These will be circulated to investigators in the trial, but sites entering participants for the first time are advised to contact Southampton Clinical Trials Unit to confirm they have the most recent version.

#### Compliance

This trial will be conducted in compliance with the approved CIP and will adhere to the principles outlined in the Medical Device Regulations 2002 (SI 2002 No.618), any subsequent amendments of the clinical trial regulations, GCP guidelines, ISO 14155:2020, the Sponsor's (and any other relevant) SOPs, and other regulatory requirements as amended.

The following terminology is used in this trial, with ISO 14155 equivalent in brackets: Chief Investigator (Principal Investigator); Sponsor (Sponsor – Legal Entity); Funder (Sponsor – Funding Entity)

#### **LIST OF ABBREVIATIONS**

AE	Adverse Event							
AMR	Antimicrobial resistance							
E&B	Encrustation and biofilm formation							
EQ 5D	Euroqol 5 dimensions (Quality of Life questionnaire)							
CI	Chief Investigator							
CIP	Clinical Investigation Plan							
CRF	Case Report Form							
CTCAE	Common Terminology Criteria for Adverse Events							
DMEC	Data Monitoring and Ethics Committee							
DMP	Data Management Plan							
GCP	Good Clinical Practice							
GFR	Glomerular Filtration Rate							
IDMC	Independent Data Monitoring Committee							
IB	Investigators Brochure							
IFU	Instructions for Use							
ISF	Investigator Site File							
ITU	Intensive Therapy Unit							
IV	Intravenous							
MHRA	Medicines and Healthcare products Regulatory Agency							
NCI	National Cancer Institute							
PCNL	Percutaneous Nephrolithotomy							
PE	Pulmonary Embolism							
PI	Principal Investigator							
PIS	Participant Information Sheet							
QOL	Quality of life							
REC	Research Ethics Committee							
SAE	Serious Adverse Event							
SAP	Statistical Analysis Plan							
SCTU	Southampton Clinical Trials Unit							
SEM/EDX	Scanning Electron Microscopy (SEM) with Energy Dispersive X-Ray Analysis							
imaging	(EDX)							
TMF	Trial Master File							
TMG	Trial Management Group							
USI-QoL	Urinary Stones and Intervention Quality of Life Measure							
USSQ	Ureteric stent symptom questionnaire							
UTI	Urinary tract infection							

## **KEYWORDS**

Novel ureteric stent, First in human, Medical Device, Quality of Life

## **CLINICAL INVESTIGATION SYNOPSIS**

Short title:	CASSETTE						
Full title:	Two single arm, multicentre unblinded first-in-human trials, including						
	phases and a qualitative substudy investigating a novel ureteric stent in						
	Kidney stone and Oncology patients to determine the reduction of						
	encrustation, biofilm deposition and complications compared to a						
	conventional JJ stent						

Phase:	First-in-human					
	Patients (male & female) aged 18 years or older with kidney stones or abdominal cancers, with previous experience of ureteric stents and clinical indication for ureteric stents.					
Population:	Inclusion criteria:  1. Aged 18 years or over  2. Ureteric stents clinically indicated either due to kidney stones or abdominal/pelvic cancers compressing ureters  3. Previous experience with ureteric stents  4. Awaiting insertion/replacement of stents  5. Able to give informed consent  6. Ability to interact with written and online study documentation  7. Sufficient English to complete study documentations and questionnaires  Exclusion criteria:  8. Expected survival <4months  9. Unfit for stent insertion  10. Unable to comply with study processes  11. Pregnancy  12. Planned stent removal is not at the same hospital as the stent					
Primary Objective:	insertion To determine rates of stent failure					
Secondary Objective:	To assess extent of encrustation and biofilm (E&B) To determine whether the novel stent leads to better clinical outcomes To assess impact of the novel stent on quality of life To understand patient experience in having the novel stent in place To understand healthcare professional experience and to understand the acceptability of the novel ureteric stent					
Tertiary Objective	N/A					

## **IDENTIFICATION AND DESCRIPTION OF THE INVESTIGATIONAL DEVICE**

[figure not shown]
Summary description of the	The investigational device (herein referred to as "Novel Ureteric Stent")					
investigational device:	consists of a ureteric stent and standard of care stent pusher. The stent					
	is a disposable, sterile, single use device that allows internal drainage of					
	urine from the kidney to the bladder. Details of the investigational					
	device are contained (or referenced) within the Investigator's Brochure					
	(IB).					
Manufacturer details:	The manufacturer of the device is University of Southampton Research					
	and Innovation Services.					
	Research and Innovation Services					
	University of Southampton					
	[name]					
	[name]					
	[name]					
	[contact]					
	Web: https://www.southampton.ac.uk/research/ris.page					
Identification of device:	Novel ureteric stents (+ a pusher) individually packaged and labelled					
	with manufacturing batch numbers and unique individual identifiers					
	per stent					

Traceability of device:	Each novel ureteric stent will be provided in individual packaging. The						
	label on the packaging will contain a batch/LOT number as well as a						
	unique identifier per stent. The unique identifier will be recorded in the						
	patient medical notes as well as on the trial database, allowing for						
	traceability of each individual stent. Full accountability of the						
	investigational devices is detailed further in Cassette Medical Device						
	Accountability Document						
B Cilled de la .	,						
Purpose of the device:	To facilitate continuous drainage of urine from the kidney to the						
	bladder. Suitable for short to long term use in patients with						
	compromised flow in the ureter						
Description of device in	The Novel Ureteric Stent (for clinical investigation sponsored by the						
contact with tissues of body	University of Southampton) contains a ureteric stent and stent pusher.						
fluids:	The stent is a flexible polymeric disposable tube with series of holes,						
	tapered tip and end tails (also known as j-tails), sterile, single use device						
	that allows internal drainage of the urine from the kidney to the						
	bladder						
Training and experience:	Detailed in section 4.4						
Training and experience:							
Medical or surgical	Detailed in section 4.5						
procedures:							
References to Investigators	Novel Ureteric Stent – Investigator Brochure						
Brochure (IB) and Instructions	Novel Ureteric Stent - Instructions for Use						
for Use (IFU):							
( - /							

#### **TRIAL SCHEMA**

## **CASSETTE** patient pathway

## **SCHEDULE OF OBSERVATIONS AND PROCEDURES**

## **KIDNEY STONE (KS) PATIENTS**

		Timepoint						
	Responsibility*1	Screening	Surgery 1	4-7 days post- Surgery 1	Within 24 hrs prior to surgery 2	Surgery 2	2-3 weeks post-Surgery 2	Qualitative interview (optional timepoint)
		(Day 0) Up to 8 weeks before surgery	Day of novel ureteric stent insertion	4-7 days post novel ureteric stent insertion	Within 24 hours prior to the novel ureteric stent removal	Day of removal of novel ureteric stent	2-3 weeks post novel ureteric stent removal	Within first month of stent removal for participants (Up to 1 month from recruitment end for clinicians)
Screening of surgery lists and								
sending PIS to potentially eligible patients	Site	x						
Informed Consent*2	Site	х	Х					
Eligibility evaluation*2	Site	х	х					
Medical History (Clinical team may review medical history to check eligibility criteria)	Site	x	x					
Check for Adverse Events/Device Deficiencies )	Site		x			х	x*3	x
Registration*2	Site	х	х					
Physical Exam*2	Site	х	Х					
KS Patient Questionnaire – BASELINE	Patient		х					
KS Patient In Situ Questionnaire	Patient			х	Х			
KS Patient Questionnaire (Post- surgery)	Patient						х	
Investigational device insertion	Study doctor		х					
Investigational device removal	Study doctor					х		
Sample collection (urine and removed novel ureteric stent)	Site					х		
Laboratory Tests (pre-op anaesthetic tests) – as required by the clinical team*4	Site	х						

CTU/FORM/5321 – Clinical Investigation Plan template for Clinical Investigations of Medical Devices (excl. IVDD) Version 1 14-DEC-2023

Endpoint analysis – weighing, cell culture, imaging	Microbiology research lab/imaging unit			х	
Endpoint analysis - Flow rate	Bioengineering lab			х	
Safety blood test (eGFR, Creatinine) – (when clinically needed) *4	Site			х	
Pregnancy Test*4	Site	х		х	
Qualitative Interview (optional)	Qualitative researcher				х

**NB:** The Participant/legal representative is free to withdraw consent at any time without providing a reason. When withdrawn, the participant will continue to receive standard clinical care. Follow up data will continue to be collected (unless the participant/legal representative has specifically stated that they do not want this to happen).

\*¹Tasks may only be performed by those suitably trained and authorised (documented on the study delegation log) to do so. Eligibility (see section 5) and assessment of safety events (see section 7) must be performed by a medically qualified doctor

\*2 Can either be completed at the screening visit or on day of surgery 1 (not required at both timepoints) – but informed consent must be obtained before all other trial procedures

\*3 Call to participant to check AE/DDs (1-3 weeks post-surgery 2)

\*4These are standard of care tests which may be performed as required at the request of the clinical team. This will only be entered in the trial database if clinically relevant.

## **ONCOLOGY (Onc) PATIENTS**

			Timepoint						
		Screening	Surgery 1	4-7 days post Surgery 1	Between Surgery 1 & 2	Within 24 hrs prior to surgery 2	Surgery 2	2-3 weeks post Surgery 2	Qualitative interview (optional timepoint)
	Responsibility* 	(Day 0) Up to 8 weeks before surgery	Day of novel ureteric stent insertion	4-7 days post novel ureteric stent insertion	Halfway between surgery 1 and surgery 2 (midpoint to be based on planned removal/repl acement date +/- 1 week)	Within 24 hours prior to the novel ureteric stent removal	Day of removal of novel ureteric stent	2-3 weeks post novel ureteric stent removal	Within first month of stent removal for participants (Up to 1 month from recruitment end for clinicians)
Screening of surgery lists and									
sending PIS to potentially eligible	Site	x							
patients									
Informed Consent*2	Site		X						
Eligibility evaluation	Site	Х							
Medical History (Clinical team may review medical history to check eligibility criteria)	Site	х	х						
Check for Adverse Events/Device Deficiencies	Site		х		x*3		х	x*3	х
Registration*2	Site	х	х						
Physical Exam*2	Site	х	х						
Onc Patient Questionnaire - BASELINE	Patient		х						
Onc Patient In Situ Questionnaire	Patient			х	х	х			
Onc Patient Questionnaire (Post- surgery)	Patient							х	
Investigational device insertion	Study doctor		х						
Investigational device removal	Study doctor					х			
Sample collection (urine and removed novel ureteric stent)	Site					х			

CTU/FORM/5321 – Clinical Investigation Plan template for Clinical Investigations of Medical Devices (excl. IVDD) Version 1 14-DEC-2023

Laboratory Tests (pre-op anaesthetic tests) – as required by the clinical team*4	Site	х				
Endpoint analysis – weighing, cell culture, imaging	Microbiology research lab/imaging unit				x	
Endpoint analysis - Flow rate	Bioengineering lab				х	
Safety blood test (eGFR, Creatinine) – (when clinically needed) *4	Site				х	
Pregnancy Test*4	Site		Х		х	
Qualitative Interview (Optional)	Qualitative researcher					х

**NB:** The Participant/legal representative is free to withdraw consent at any time without providing a reason. When withdrawn, the participant will continue to receive standard clinical care. Follow up data will continue to be collected (unless the participant/legal representative has specifically stated that they do not want this to happen).

\*¹Tasks may only be performed by those suitably trained and authorised (documented on the study delegation log) to do so. Eligibility (see section 5) and assessment of safety events (see section 7) must be performed by a medically qualified doctor

\*2 Can either be completed at the screening visit or on day of surgery 1 (not required at both timepoints) – but informed consent must be obtained before all other trial procedures

\*3 Call to participant to check AE/DDs midway between surgery 1 and surgery 2 and 1-3 weeks post-surgery 2

\*4 These are standard of care tests which may be performed as required at the request of the clinical team. This will only be entered in the trial database if clinically relevant.

#### 1 INTRODUCTION

#### 1.1 BACKGROUND

Ureteric stents and catheters are deployed clinically as temporary measures to restore urinary drainage, in patients with kidney stones, tumours and strictures. Prevalence of these increases with age [1]–[4]. Device-associated encrustation and biofilm formation (E&B) are key complications, leading to urinary tract infections (UTIs) in >90% of stents [5], causing stent blockage and favouring development of antibiotic resistance.

UTIs are a significant cause of morbidity, especially among the elderly population, with 4,835 deaths in England and Wales reported in 2012 [6]. The National Institute for Health Research (NIHR, 2016) reported that 1-3% of all primary care consultations concern UTI-related symptoms, leading to 13.7% of antibiotic prescriptions globally. The report also revealed that >92m people globally are diagnosed with UTIs annually [7].

Urological device-associated infections significantly compromise patient' quality of life and the effectiveness of services, imposing a £2.5b annual burden on the NHS [8]. Patients' exposure to hospital environment and general anaesthetic use impact on Quality-of-Life (QoL), resulting in unnecessary hospital bed-nights. We have developed a novel urological stent associated with significantly reduced particle deposition, potentially extending the stent's lifetime, resulting in reduced hospitalisation and improved QoL.

Urological stents and catheters often lead to inflammation, causing pain and infection in the urinary tract [7]. Moreover, 80% of stents are associated with pain, negatively impacting on QoL [9] and mental health. Offering novel designs with significantly lower E&B leads to a reduction in UTIs and improves QoL. Reducing hospital admissions (from 3 to 1 per patient, annually) would free >100,000 bed-nights, allowing the elderly to regain independence. Our proposed research could have a significant impact towards fulfilling the 'healthy ageing' Grand Challenge. Additionally, the novel stent reduces prevalence of infections and therefore, of antibiotic prescriptions contributing to the Global Antimicrobial Resistance (AMR) challenge.

Considering only onco-urological patients, >30,000 stents are inserted every year across 200 NHS units. Due to stent failures, each patient undergoes 3 to 6 replacements, resulting in >90,000 stent replacements. Under the current tariff-based system, hospitals are paid for each intervention, costing the NHS >£3,500, bringing the total cost of replacements to ~£315m annually. Unnecessary replacements increase the number of bednights and use of anaesthetics. A longer-lasting stent means that each patient comes to the hospital ideally only once, reducing their exposure to the hospital environment and anaesthetic-associated risks. Additionally, under the current model hospitals would improve their quality of service and save at least 2 bed-nights per patient. The NHS is moving towards a "block contract" model, meaning that hospitals will receive a lump sum for the year, and they'll regularly monitor budgets and improve cost efficiency where possible. Improved stents will allow the same urology budget to deliver more healthcare, reducing theatre time for stent insertion and replacement. Our innovative stent design offers a potential annual saving of >£210m for the NHS, allowing hospitals to reallocate their resources. Today E&B is still a major determinant of stent failure and associated side effects. We aim to address this challenge through our novel stent, and if equivalent safety and improved efficacy are demonstrated, anticipate market launch via third-party suppliers 2-3 years post project.

Solutions to break this pathway (stent presence leading to inflammation, pain and infection) have been developed, including stent construction materials (e.g. metallic alloys, polymers, biodegradable and drug-eluting materials), stent coatings (e.g. heparin, chitosan, hydrogel, carbon) and alternative stent shapes (e.g. double-J, loop, mesh, string, expandable), to improve the efficacy and safety of stents [10]–[13]. Despite all these advances, there is still a significant prevalence of E&B [14]–[16]. This is also due to the lack of studies correlating fluid dynamic metrics with deposition of particles causing E&B. The lead applicant's PhD

investigated the mechanisms of particle deposition in urological stents, and successfully determined fluid dynamic parameters governing particle deposition on ureteric stents and catheters. His research led to developing a stent with specially shaped side-holes that prevent stagnation points (i.e., areas of low flow that cause particles to settle and E&B). These developments demonstrated >80% reduction in particle deposition at side-holes, in-vitro [17], [18]. Their innovative architecture can be implemented on stents and catheters. The technology, including the stent design and manufacturing process, is protectable — Patent# WO2019048860A1, WIPO(PCT). These results were further validated in an animal study (6 pigs: 3 novel-design stents vs 3 conventional-design stents for a 4-week period) at Stone Centre at Vancouver General Hospital (VGH), a centre of excellence in animal studies on urological products. The study (available upon request) concluded that the functionality of stents with novel side-holes is the same as that of standard stents in terms of safety. Specifically, the novel stent does not result in increased risk of irritation, inflammation and hydronephrosis [19]. Furthermore, Scanning Electron Microscopy (SEM) with Energy Dispersive X-Ray Analysis (SEM/EDX) imaging showed that the novel design decreased the build-up of particles on the stent surface. Thus, it demonstrated significant potential for the new side-hole configuration to change patterns of particle deposition on the stent's surface, decreasing encrustation.

## 1.2 BENEFITS AND RISKS OF THE INVESTIGATIONAL DEVICE, CLINICAL PROCEDURE, AND CLINICAL INVESTIGATION

#### 1.2.1 Anticipated clinical benefits

This study provides participants an opportunity to benefit from the novel ureteric stent which should be less prone to blockages. Anticipated clinical benefits relating to reductions in UTIs, pain, number of surgeries and exposure to possible hospital-acquired infections are described throughout section 1.1.

#### 1.2.2 Anticipated adverse device effects

- During insertion difficulty advancing because of stent buckling on the side hole. If this happens, it can increase the operation time by 5 mins.
- During removal stent fracturing on the side holes, which could increase the chance of needing a surgery (ureteroscopy or even a Percutaneous Nephrolithotomy (PCNL) or a second operation).
- Encrustation and biofilm formation (E&B) leading to failure to drain. Clinical judgement will be required for each incidence, to determine whether this is the outcome of the new design or not.
- Functional challenges (failing to drain or it is not doing what it is supposed to do). Evidenced by change earlier
  than planned (for oncology participants), need for additional surgical or radiology intervention (could be
  anything beyond the planned normal) or "kidney failure" (evidenced by AKI (Acute kidney injury) on blood tests
  (eGFR / Creatine kidney functioning tests) and/or WORSENING of hydronephrosis on Imaging oncology).

### 1.2.3 Risks associated with participation in the clinical investigation

Risks associated with participation in the clinical investigation are not expected to be beyond those associated with standard of care for stent insertion in these patient groups. Risks associated with the device are detailed in section 1.2.2 as expected device effects. Risks relating to patient safety are detailed in the Investigators' Brochure, and are summarised below:

- Cystitis/UTI (urinary tract infection) and associated symptoms
- Stent bother
- Haematuria
- Loin pain

All risks associated with participation in the clinical investigation have been assessed and documented in the Trial Risk Assessment as appropriate.

#### 1.2.4 Possible interactions with concomitant medical treatments as considered under the risk analysis

The novel ureteric stent is compatible with (and would not require any deviation from the routine plan for) all forms of imaging, any medication, and any surgical intervention.

#### 1.2.5 Steps that will be taken to control or mitigate the risks

- If it is difficult to advance because of stent buckling on the side hole, then a stiffer wire is to be used (as is standard practice) or stent will be changed to a different one (either new investigational device or standard stent, as decided by clinician) to reduce the risk. This, if happens, can increase the operation time by 5 mins.
- If the participant experiences functional challenges with the stent (the stent failing to drain or work as expected), and required additional intervention (i.e. draining kidney by alternative means e.g. nephrostomy, alternative stent), then pause this participant's involvement (as decided by clinician) and analyse/investigate as per stop/go criteria (see section 3.1)
- Due to the novel nature of the investigational device, stopping criteria (see section 3.1) have been included in the trial design to monitor and assess the events listed in section 1.2.2

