## 2.2 PRIMARY TRIAL OBJECTIVE AND ENDPOINT

The primary endpoint is stent failure, defined as any of:

- a) a stent change earlier than planned (oncology only);
- b) need for stent related additional surgical or radiological intervention;
- c) kidney failure and/or worsening hydronephrosis.

No intercurrent events (events that would affect the collection or interpretation of stent failure data) are thought likely to occur.

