#### 3.1 STOPPING CRITERIA

Table 1 - Stopping rules for kidney stone patients

Criteria	Criteria (1)	Criteria (2)
Event	Rule following 10	Rule following 25
	patients	patients
Insertion (not severe) – clinical judgement: If it is difficult		
to advance because of stent buckling on the side hole,		
then a stiffer wire is used as standard method or stent will		
be changed to		
	Stop/pause and	Stop/pause and
Alternative stent (same make / design but different	investigation if >4 patients	investigation if >10
size French calibre or length) E.g. novel stent 6Fr /	affected	patients affected in total
22cm changed to a novel stent 8Fr 24cm (Not a STOP)		
Different Stent (a different make/design of stent		
regardless of calibre or length) E.g. novel stent 6Fr /		
22cm changed to a Boston 6Fr / 22cm (It is a STOP)		

to reduce the risk. This, if happens, can increase the operation time by approximately 5 mins.		
Removal (could be severe) – clinical judgement: if stent fractures on the side holes, which could increase the chance of needing a surgery (ureteroscopy or even a Percutaneous Nephrolithotomy (PCNL) or a second operation). This is the main reason for pausing the trial until investigation of whether the stent was the cause.	Stop/pause and investigation if >2 patients affected	Stop/pause and investigation if >5 patients affected
Removal of stent <7 days of insertion due to severe infection, overwhelming symptoms, or failure to drain (clinical judgment)	Stop/pause if >4 patients	Stop/pause if >4 patients

If no safety and efficacy concerns are found in the kidney stone patient group (following criteria 1), recruitment of cancer patients admitted to either the University College London Hospital (UCLH) or University Hospital Southampton (UHS) for management of urine drainage in ureter will commence. The cancer patient group will also be assessed for safety signals one week after the 10th patient has had their stent inserted. Another safety assessment of the same cohort will also take place once a further 15 patients have been recruited (25 in total). Recruitment will not be paused during this time.

Table 2 - Stopping rules for cancer patients

Criteria Event	Rule up to the first 10 patients	Rule up to the next 15 patients (ie. 25 in total)
Insertion (not severe) – clinical judgement: If it is difficult to advance because of stent buckling on the side hole, then a stiffer wire is used as standard method or stent will be changed to		

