#### 8.4 INTERIM ANALYSIS

No formal statistical testing at an interim stage is planned. For both the kidney stone and oncology cohorts, there will be an assessment of safety after 10 participants have had the stent removed. There is a safety assessment after the 25 kidney stone patients and up to 15 oncology patients have had the stent removed. See section 3.1 for full details.

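### Section 1.2.5 relies on stopping criteria that section 3.1 does not contain: drainage or functional failure triggers no trial-level stop or pause unless the stent is removed within 7 days

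*Protocol*

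**What the plan says.** Section 1.2.2 lists four anticipated device effects: buckling at insertion, fracture at removal, "Encrustation and biofilm formation (E&B) leading to failure to drain", and functional challenges. The last is evidenced by an early change (oncology), additional intervention, acute kidney injury or worsening hydronephrosis. Neither of the last two effects carries a time limit.

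Section 1.2.5 makes two links to section 3.1. It says in general that "stopping criteria (see section 3.1) have been included in the trial design to monitor and assess the events listed in section 1.2.2". For a functional failure needing another means of drainage, with nephrostomy given as an example, it pauses that participant and says to "analyse/investigate as per stop/go criteria (see section 3.1").

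Tables 1 and 2 in section 3.1 each have three rows: insertion difficulty, fracture at removal, and "Removal of stent <7 days of insertion due to severe infection, overwhelming symptoms, or failure to drain (clinical judgment").

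On timing, section 3.1 says: "The cancer patient group will also be assessed for safety signals one week after the" tenth insertion, and again "once a further 15 patients have been recruited (25 in total"). Section 8.4 says that for both cohorts "there will be an assessment of safety after 10 participants have had the stent removed", with a later review after the 25 kidney stone removals and up to 15 oncology removals. Planned dwell is up to 4 weeks (kidney stone) or about 25 weeks (oncology), per section 3.

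**The concern.** The protocol names a risk, says that a stopping criterion controls it, and cites the section where the criterion should be. For drainage and functional failure that section holds a criterion for the first week only. The uncovered events are primary-endpoint events in a first-in-human device: section 2.2 counts early change in oncology, "need for stent related additional surgical or radiological intervention", and kidney failure or worsening hydronephrosis. Section 4.4 advises limiting dwell to under 6 months to reduce encrustation, so this risk belongs largely to the later period that the tables leave out.

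At stake is whether an accumulation of late failures would prompt a trial-level pause by rule, or only if someone judged it necessary. Oncology recruitment continues through its reviews, so the rule matters most in that cohort.

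**Working it through.** The plan states no operating figure for its stopping criteria, so there is none to reproduce. The check is a match of the text, then arithmetic on dwell and look times.

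**1. Events in 1.2.2 against the rows of Tables 1 and 2**

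| Event in 1.2.2 | Row in 3.1 | Covered |
|---|---|---|
| Buckling at insertion | Insertion: >4 of 10, >10 of 25 | Yes |
| Fracture at removal | Fracture: >2 of 10, >5 of 25 | Yes |
| Encrustation and biofilm, failure to drain | Early-removal row only | Only if removed before day 7 |
| Functional challenges | Early-removal row only | Only if removed before day 7 for failure to drain, severe infection or overwhelming symptoms |

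No row counts drainage failure from day 7 on, failure managed with the stent left in place, acute kidney injury or worsening hydronephrosis without removal before day 7, or an early oncology change at or after day 7.

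**2. Share of planned dwell inside the window**

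- Kidney stone: 7 / (4 × 7) = 7/28 = 25%.
- Oncology: 7 / (25 × 7) = 7/175 = 4%.

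**3. What the count can detect**

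If no failure leads to removal before day 7, the early-removal count is zero and the chance of a trigger is zero at any failure rate. In the extreme, 25 of 25 stents failing to drain after day 7 without fracture, and with no insertion difficulty, would meet no row. This needs no assumed rate.

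**4. Oncology look times**

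| | Section 3.1 | Section 8.4 |
|---|---|---|
| First | One week after 10th insertion | After 10 removals |
| Second | At 25 recruited | After up to 15 removals |

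With a dwell of about 25 weeks these are different dates.

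**5. Dwell seen at the 3.1 looks**

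The protocol gives no oncology accrual curve. Assume 25 evenly spaced insertions over R weeks, hence R/24 weeks apart, and a planned dwell of 25 weeks.

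First look: mean dwell = 1 + 4.5 × R/24; longest dwell = 1 + 9 × R/24.

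- R = 26: mean 5.9 weeks, 5.875/25 = 23.5%; longest 10.75 weeks.
- R = 39: mean 8.3 weeks, 8.3125/25 = 33%; longest 15.6 weeks.
- R = 52 (the whole 12-month recruitment period, an outer bound because oncology starts after the kidney stone review): mean 10.75 weeks, 43%; longest 20.5 weeks.

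In all three cases 0 of 10 have reached planned removal.

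Second look, at week R: mean of the smaller of 25 and k × R/24, for k = 0 to 24.

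- R = 26: (13 × 25 − 1)/25 = 12.96 weeks, 52%; 1 of 25 at planned removal.
- R = 39: (1.625 × 120 + 9 × 25)/25 = 420/25 = 16.8 weeks, 67%; 9 of 25.
- R = 52: (2.1667 × 66 + 13 × 25)/25 = 468/25 = 18.72 weeks, 75%; 13 of 25.

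**6. Would a look after 10 oncology removals, as in 8.4, suffice?**

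The 10th planned removal falls at 25 + 9R/24 weeks, and the last insertion at R.

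- R = 26: 34.75 − 26 = 8.75 weeks after the last insertion.
- R = 39: 39.6 − 39 = 0.6 weeks after.
- R = 52: 44.5 − 52 = −7.5, that is 7.5 weeks before.

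The two coincide when 25 = 15R/24, at R = 40. Whether that look could protect enrolment therefore depends on accrual, which favours continuous counting.

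**The case against.** The strongest reply is that late failures are watched by other routes. Section 7.4.1 lists both kinds of drainage failure as device deficiencies. Section 7.2.2 requires each to be assessed for whether it might have led to a serious event, and 7.5.1.3 sends those that might have to the MHRA. Under 7.6.3 the other site's principal investigator reviews every serious adverse event, and 7.6.4 passes safety data to the monitoring committee. The committee in 12.2 watches the main outcomes. Oncology opens only if the kidney stone review raises no safety or efficacy concern. Kidney stone reviews follow removal, so they see full dwell. The committee charter, Trial Monitoring Plan and Trial Risk Assessment are not shown and may say more.

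All of this stands, so a reader who infers that late failures would go unnoticed goes too far. But these routes work case by case or by general remit. The oncology gate is tied to criteria 1, the same Table 1 rows. None is the criterion that 1.2.5 says is in 3.1.

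A second reply is that judgement is the intended design: the table rows invoke it, and 1.2.2 asks for it on each encrustation failure. That is a fair reason to build attribution into any new row. It does not repair the cross-reference.

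Third, 8.4 ends by deferring to 3.1 for details, which suggests that 3.1 governs. If so, the governing looks are the early ones.

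A reader might also take the kidney stone early-removal limit at 25 patients (>4, against >10 in total for oncology) for an error, since the other limits keep their proportion from 10 to 25 patients. The documents do not support that: a stricter limit in the first-exposed cohort may be intended. It is a separate point to clarify and adds no weight here.

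**Conclusion.** The contradiction holds on the text alone. Section 1.2.5 claims coverage of four events. Section 3.1 fully covers two and covers the other two only through removal in the first 7 days, about 25% of kidney stone dwell and 4% of oncology dwell. Later failures, and failures managed without removal, trigger no trial-level stop or pause in section 3.1. The conflict between 3.1 and 8.4 on oncology looks is also textual. The share of dwell seen at those looks (23% to 33%, then 52% to 67%) rests on even accrual over an assumed 26 to 39 weeks, but the finding of 0 of 10 at planned removal at the first look holds even at 52 weeks.

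This should be fixed by amendment. It does not show that participants are unmonitored, and it does not affect the primary estimate of the failure rate. The documents give no failure rates, so no probability of a missed stop can be stated for this trial.

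**What to change.** In one protocol amendment:

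- Add one row to Tables 1 and 2 for section 2.2 stent failures at any time in dwell that are judged possibly, probably or causally device-related on the section 7.3 scale and are not already counted in another row. This keeps the clinical judgement step of 1.2.2.
- Exclude removals because the stent is no longer needed, which 6.8.1 treats as success, and changes due to disease progression, which 6.8.1 permits.
- Let the clinical team and the safety committee set the limit.
- Count the row continuously, so that it does not depend on the early oncology looks.
- Give the same look times in 3.1 and 8.4.
- Correct 1.2.5 to describe what the tables then cover.

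Correcting 1.2.5 alone would remove the contradiction but leave late failure without a trigger. The cost is a running tally of an endpoint already being collected, an attribution decision for each failure, and possibly one extra review pause. Separately, state whether the kidney stone >4 at 25 patients is cumulative and confirm that the stricter limit is intended.
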